#### 4.2 Exclusion Criteria

Candidates meeting any of the following criteria at baseline will be excluded from participation:

- Participation in formal or organized yoga classes or instruction within the past 3 months; or any prior yoga therapy directed specifically at improving urinary incontinence or pelvic floor dysfunction
- Participation in at least weekly organized physical conditioning classes or instruction in the past 3 months involving muscle stretching and strengthening exercises (not including aerobic classes that do not emphasize stretching or strengthening).
- Currently pregnant (by self-report or screening urine pregnancy test), gave birth within the past 6 months, or planning pregnancy during the study period (approximately 2 to 6 months)
- Current urinary tract infection (screening dipstick urinalysis with leukocyte estrace, nitrites or blood) or a history of 3 or more urinary tract infections in the preceding year
- Report history of neurologic conditions such as stroke, multiple sclerosis, spinal cord injury, or Parkinson's disease, or a lumbosacral spine condition associated with neurological symptoms
- Unable to walk up a flight of stairs or at least 2 blocks on level ground without assistance (i.e., functional capacity < 4 METs)
- Unable to get up from a supine to a standing position in 10 seconds or less and without assistance
- Morbid obesity defined by a measured body mass index of  $>40 \text{ kg/m}^2$  at the screening evaluation.
- Report any history of prior anti-incontinence or urethral surgery (not including urethral dilation), pelvic cancer, or pelvic irradiation for any reason
- Report use of bladder botox, electrostimulation, bladder training, or pelvic floor exercise training (with certified practitioners) in the past 3 months
- Report other surgery to the pelvis (hysterectomy, oophorectomy, vaginal surgery, bladder surgery, colon surgery) within the past 3 months
- Report use of medications with the potential to affect incontinence (anticholinergic bladder medications, tricyclic antidepressants, selective norepinephrine reuptake inhibitors, mirabegron, loop diuretics) within the past month
- Report starting stopping, or changing the dose of a medication with the potential to affect anxiety or stress symptoms (i.e., selective serotonin reuptake inhibitors, anxiolytics/sedatives, antipsychotics) within the past 1 month, or plans to start, stop, or change to dose of such a medication during the study period

- Report use of medical devices (i.e. pessary) for incontinence within the previous month (participants may stop use of device and re-present for study)
- Report history of interstitial cystitis, fistula or hole in bladder or rectum, or birth defect leading to urine leakage
- Report symptomatic pelvic organ prolapse (assessed using a standardized question, “Have your pelvic organs (uterus, bladder, or rectum) been dropping out of your vagina causing a feeling of bulging, pressure, or protrusion or a sensation like your “insides are coming out”?”)
- Report history of vulvodynia, chronic pelvic pain, or pain when practicing pelvic floor exercises
- Report conditions that, in the judgment of the investigators, render potential participants unlikely to follow the protocol, including plans to move, substance abuse, significant psychiatric problems, or dementia
- Participation in another research study that involves investigational drugs or devices that could potentially confound the results of this study
- Unable to understand study procedures, complete study interviews, or provide informed consent in English

#### **4.3 Study Enrollment Procedures**

Recruitment: Participants will be recruited from the greater San Francisco Bay area using a multi-component approach that has been employed successfully in past clinical trials led by the investigators. This includes community-based media efforts (newspaper and radio advertisements, notices posted in community and senior centers, mass community mailings), recruitment from a database of women who have given permission to be contacted for women’s health research studies based at the University of California San Francisco, and posting of recruitment fliers in clinician offices (such as general internal medicine, geriatrics, gynecology, or alternative medicine).

Recruitment will be organized in waves to assemble successive cohorts of women who are confirmed to meet all eligibility criteria and who are available to attend upcoming group yoga or physical conditioning classes. Based on past experience, the investigators assume that three waves will be needed to recruit and randomize at 60 eligible participants, with up to three months of recruitment required per wave, and 15 to 20 eligible women randomized in each wave. This will allow for a minimum of ~8 women taking part in each class series in each intervention group.

Screening: Preliminary eligibility will be determined by research coordinators through a Screening Telephone Interview followed by an in-person Screening Clinic Visit. During the Screening Telephone Interview, coordinators will follow a standardized screening interview script to assess preliminary eligibility related to age, gender, incontinence history, and exclusionary conditions and medications and document reasons for ineligibility on the screening interview form (see section 6.2.3, Screening Procedures, for more detail). Candidates who appear preliminarily eligible at the end of the screening telephone interview will be scheduled to attend an in-person Screening Clinic Visit. After providing written informed consent at this visit, women will undergo more detailed assessment of incontinence symptoms, use of clinical incontinence therapies, exclusionary medical conditions, exclusionary medications, urine dipstick and pregnancy testing (for women of childbearing potential), and brief physical function assessment (see description of study procedures below), with reasons for eligibility or ineligibility documented on the screening clinic intake form.

At the end of the Screening Clinic Visit, women who appear eligible will be given a blank voiding diary and instructions for completing it at home over a 3-day period and returning it to study staff at a Baseline Clinic Visit. Those who are confirmed to have stress-predominant, urgency-predominant, or mixed urgency-stress incontinence occurring at least 3 times over the 3-day diary period and meet all other inclusion/exclusion criteria at the Baseline Clinic Visit will be considered eligible for randomization to one of the two intervention groups.

**Randomization:** During each recruitment/randomization wave, eligible women will be randomized in a 1:1 ratio to one of the two intervention groups. Randomization will be stratified by clinical type of incontinence (i.e., stress, urgency, or mixed), to ensure adequacy of randomization within these three types. Randomization will be implemented by computer algorithm using randomly permuted blocks of sizes 2 and 4, with proof of eligibility required before assignment. To avoid manipulation, standard allocation concealment procedures will be followed (see section 6.2.4. on Randomization for more detail).

To avoid excessive lag time between randomization and the start of the yoga therapy or physical conditioning programs, randomization will take place within two weeks of the yoga or physical conditioning program orientation session. For candidates whose Baseline Clinic Visit falls within this two-week window, randomization will take place directly at the Baseline Clinic Visit. For candidates who complete their Baseline Clinic Visit more than two weeks before the start of the yoga or physical conditioning intervention programs, a Randomization Telephone Call will be scheduled to complete randomization within the two-week window.

## 5. STUDY INTERVENTIONS

### 5.1 Yoga Therapy Program

**Overview and rationale:** The 12-week yoga therapy program will provide instruction and practice in a variety of yoga postures and techniques that have been selected by the study yoga expert consultants for their potential to improve bladder control and safety and feasibility for the target population. The study will feature a therapeutic program based primarily on Iyengar yoga, a form of Hatha yoga that is known for its potential therapeutic applications, has been employed successfully in other studies of yoga for different indications, and differs from other Hatha yoga styles (power yoga, bikram yoga) in multiple ways that are likely to maximize both efficacy and safety for this study. These include: 1) emphasis on precise anatomical and postural alignment during practice of yoga postures; 2) incorporation of props to minimize risk of injury and accommodate those with lower strength or flexibility; 3) emphasis on mindful awareness during practice of postures rather than rapid cycling through postures. The resulting yoga program, which was pre-tested and refined in the investigators' pilot LILY trial, is designed to maximize women's awareness of and control over the pelvic floor and improve underlying stress and anxiety, while still being feasible for ambulatory women across a wide range of ages, as well as grounded in techniques common to Iyengar yoga at large.

**Content and postures:** The study yoga program will focus on a core set of 14 postures that are widely used in yoga practice, have been pre-tested in the investigators' earlier pilot study, and can be safely adapted for ambulatory women of all ages, including those with moderately decreased flexibility or mobility. These

include both active postures engaging the pelvic floor and more passive postures promoting relaxation: Baddha Konasana (bounded angle pose), Bharadvajasana (seated twist pose), Malasana (squat pose), Parsvokonasana (side angle pose), Parsvottasana (intense side stretch pose), Salabhasana (locust pose), Savasana (corpse pose), Salamba Set Bandhasana (supported bridge pose), Supta Buddha Konasana (reclined cobbler's pose), Utkatasana (chair pose), Supta Padagushthasana (reclined big toe pose), Tadasana (mountain pose), Trikonasana (triangle pose), Viparita Karani Variation (legs up the wall pose), and Virabhadrasana 2 (warrior 2 pose).

**Staff qualifications and training:** Each yoga therapy class series will be led by a primary instructor who will: 1) have at least 2 years of experience teaching yoga in the community; 2) review a detailed, study-specific written instructor manual describing all of the postures and yoga techniques to be used in the study program; 3) complete at least 2 hours of in-person training in study-specific techniques with one of the study yoga expert consultants ([name] or [name]); 4) complete study-specific training in documentation of participant attendance, review of home practice logs, and recording of yoga postures practiced during group classes on appropriate study forms; 5) carry and submit proof of personal liability insurance (minimum of \$2 million coverage); and 6) confirm his or her willingness to adhere to the study intervention procedures. To maximize the generalizability of the study results and minimize observed effects due to specific providers, different primary instructors will be sought for each yoga class series. For each class series, a back-up instructor will also be identified who can teach a class in the event that the primary instructor is ill or is unable to teach due to an emergency.

**Orientation and classes:** Prior to group instruction, participants in each class series will attend a 90-minute group orientation led by an appointed class instructor. This will include an overview of the general principles of Iyengar yoga, an orientation to the structures of the pelvis, spine, and lower extremity, and an introduction to the yoga postures and the props to be used in the study. After the orientation, women will attend 90-minute group classes twice weekly for 12 weeks, led by the same instructor as well as an assistant to provide personalized attention to students.

During group classes with an expected size of 8 to 15 participants, the instructor will guide women in practicing yoga postures, calling attention to ways in which postures can improve pelvic floor function and adapt postures to accommodate physical limitations. Women will also be taught to avoid habits that may worsen incontinence during practice, such as squeezing of abdominal rather than pelvic muscles.

Following a study-specific guide, instructors will gradually introduce postures as classes progress, with the goal of making participants comfortable with all core postures by the end of 8 weeks and fully confident in performing postures by 12 weeks.

**Home practice:** In addition to attending group classes, participants will be asked to practice yoga at home at least one additional time per week and will be given a diary to keep track of the dates and times of practice. Women will also be given a written manual, pre-tested in the pilot LILY study, that includes pictures and descriptions of each yoga posture to guide them in home practice. Each participant will be given a limited set of yoga props (a mat, belt, and 2 blocks) for home practice. Women will be encouraged to practice with other members of their classes, but will be discouraged from practicing with individuals who are not in their class and from taking part in non-study yoga activities that might dilute study techniques. After the

end of the main 12-week study period, participants will be encouraged to continue practice yoga at least one hour per week at home, although they will not continue to attend study-specific group classes.

**Quality and safety:** The study program will incorporate multiple modifications to help women across the age range to perform postures in ways that minimize risk of muscle strain or injury. Participant manuals will include specific instructions on adapting each posture and/or using props to accommodate problems with mobility, flexibility, or balance. To promote quality and safety, the instructors leading classes will be required to have at least 2 years of experience teaching yoga and have completed dedicated, study-specific training with the study's expert consultants. Following procedures established in the pilot study, a consultant will visit at least one class in each series to ensure that postures are being taught according to protocol, evaluate students' success in learning yoga, and ensure fidelity across instructors. Monthly conference calls will be conducted to help instructors trouble-shoot issues that arise in instruction.

## 5.2 Physical Conditioning Control Program

**Overview and rationale:** This trial will include a 12-week physical conditioning program that will provide a rigorous time-and-attention control for the yoga program, but has been designed to avoid engaging the pelvic floor or promoting mindful relaxation. To minimize differential expectations of treatment success, women will be told that they are enrolling in a study of two different types of low-impact physical activity-based interventions (yoga versus physical conditioning) to enhance management of incontinence. Physical conditioning exercises have been adapted from exercises used in prior studies conducted by the investigators, such as the PRYSMS trial of restorative yoga vs. stretching for metabolic syndrome (designed by [name], DPT, consultant on this proposal), in which participants maintained good adherence to the stretching program despite a long study period. Similar to postures in the yoga therapy program, the exercises in the physical conditioning program have been selected for their potential to be performed safely by women across a range of ages and flexibility levels.

**Content and exercises:** After a brief education about sitting and standing posture, the physical conditioning program will focus on a core set of stretching/strengthening exercises that will be performed sitting in a chair: levator scapulae, upper trapezius, scalenes, shoulder horizontal adduction, triceps, pectoral stretch with hands behind head, wrist flexors and extensors, trunk flexion, trunk extension, trunk side-bend, trunk rotation, and hamstring stretches. Additional chair exercises will incorporate a stretching strap: pectoral stretch with strap, gastrocnemius stretch with strap, and hand behind back with strap. A few stretches will be performed on an exercise mat on the floor: supine single knee to chest, supine hamstrings stretch with strap, quadriceps stretch with strap, supine shoulder flexion with stretch strap, and seated adductor stretch. Three exercises will be performed in the standing position: gastrocnemius, soleus, shoulder flexion, and shoulder abduction stretches.

**Staff qualifications and training:** Each physical conditioning class series will be led by a primary instructor who: 1) is either certified as a personal trainer through the National Academy of Sports Medicine or the American College of Sports Medicine, or licensed as a physical therapist by the Physical Therapy Board of California; 2) has at least 2 years of experience working as a physical therapist or physical trainer in either individual or group settings; 3) will have reviewed a detailed, study-specific

training manual describing all of the stretching/strengthening exercises to be used in the study program; 4) will have completed at least 2 hours of in-person training in study-specific techniques with study expert consultant [name], DPT; 5) will have completed study-specific training in documentation of participant attendance, review of home practice logs (for adherence), and recording of exercises performed during group classes on appropriate study forms; 6) carries and submits proof of personal liability insurance (minimum of \$2 million coverage); 7) confirms his or her willingness to adhere to the study intervention procedures. To maximize the generalizability of the study results and minimize observed effects due to specific providers, different primary instructors will be sought for each class series. For each class series, a back-up instructor will also be identified who can teach a class in the event that the primary instructor is ill or is unable to teach due to an emergency.

**Group orientation and classes:** Similar to the yoga therapy program, the physical conditioning program will begin with a group orientation led by a physical therapist or trainer and an assistant, who will provide an overview of the stretching/strengthening exercises to be covered in the program. This will be followed by 90-minute twice weekly group classes, each with 8 to 15 participants, led by the same therapist and assistant, who will have received in-person study-specific training from consultant [name], DPT. Classes will be designed to make women comfortable with all stretching/strengthening exercises by 8 weeks and fully confident in performing exercises by 12 weeks.

**Home practice:** In addition to attending group classes, women will be asked to perform stretching/strengthening exercises at home at least one additional time per week and record the dates and times of practice in a log. Women will receive a detailed manual with pictures and descriptions of each stretching/strengthening exercise to guide them in home practice, as well as a stretch strap and exercise mat to use at home. After the end of the main 12-week study period, participants will be encouraged to continue practice stretching/strengthening exercises at least one hour per week at home, although they will not continue to attend study-specific group classes.

**Quality and safety:** Instructors leading physical conditioning classes will be physical therapists or trainers who have at least 2 years of experience working with adults of a range of ages and have completed dedicated in-person training with [name], DPT. [name] will provide quality monitoring and assess women's success in learning stretching/strengthening exercises by making an in-person visit to at least one class in each series. She will also lead monthly conference calls with instructors, similar to quality monitoring for the yoga program.

## **5.3 Concomitant Interventions**

### **5.3.1 Required Interventions**

Participants in both intervention groups will also receive a pamphlet at the Baseline Clinic Visit that provides basic patient-directed information about first-line behavioral self-management of incontinence, including pelvic muscle exercises, timed urination, and urge suppression. This pamphlet is consistent with usual care of incontinence in the general community, and has been used in previous studies of experimental treatments for incontinence conducted by the investigators. Since information about behavioral self-management of incontinence is available from multiple websites and public resources,

systematic provision of this information will help avoid differential use of self-management techniques between treatment groups, and will also reflect expected concomitant use of these techniques with yoga in clinical practice. Participants will be queried about use of these techniques at baseline, at the 8-week and 12-week clinic visits, and as part of the 24-week assessment, so that information about co-interventions can be incorporated into data analyses if appropriate.

### **5.3.2 Prohibited Interventions**

Participants will be asked to refrain from using other clinical treatments for incontinence during the 12-week intervention period as well as the 12-week post-treatment follow-up period. These include medications with the potential to affect incontinence symptoms (anticholinergic bladder medications, selective norepinephrine reuptake inhibitors, tricyclic antidepressants, mirabegron), invasive or surgical bladder treatments, medical devices used to improve bladder symptoms (e.g., pessary), and behavioral treatment programs administered by certified practitioners (e.g., pelvic floor rehabilitation therapy, biofeedback programs). Additionally, participants will be asked to refrain from starting or changing the dosage of medications that could affect anxiety and perceived stress symptoms (e.g., antidepressants, sedatives/hypnotics, or antipsychotic agents), although maintenance of stable dosages of these medications will be acceptable.

Participants will be queried about use of these prohibited interventions at baseline, at the 8-week and 12-week clinic visits, and as part of the 24-week assessment. If participants are found to be using prohibited interventions, they will not be required to terminate the study early, but study staff will also re-urge participants to avoid using prohibited interventions if at all possible (although this may not be possible for some types of interventions), and information about use of prohibited interventions can be taken into account in data analyses.

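### Non-study yoga is discouraged after randomization only in the yoga arm, and no specified follow-up item asks control women about it, so a narrowing difference at week 24 could not be told from a fading effect

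*Combined protocol and SAP*

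**What the plan says.** Before entry, Section 4.2 excludes women for "Participation in formal or organized yoga classes or instruction within the past 3 months", and separately for "Participation in at least weekly organized physical conditioning classes or instruction in the past 3 months".

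After randomization, the instruction to the yoga arm in Section 5.1 (Home practice) is that women are "discouraged from practicing with individuals who are not in their class and from taking part in non-study yoga activities that might dilute study techniques". The matching paragraph for the control arm in Section 5.2 asks women to "perform stretching/strengthening exercises at home at least one additional time per week and record the dates and times of practice in a log" and is silent on outside yoga.

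Section 5.3.2 applies to both arms. It opens: "Participants will be asked to refrain from using other clinical treatments for incontinence during the 12-week intervention period", and it extends the request over the 12 weeks after treatment. The items are bladder-active drugs, invasive or surgical treatment, devices, and "behavioral treatment programs administered by certified practitioners (e.g., pelvic floor rehabilitation therapy, biofeedback programs". A further sentence covers medication for anxiety and stress. The follow-up query in that section concerns the listed interventions. The query in Section 5.3.1 concerns the self-management techniques in the pamphlet.

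The table in Section 6.2.7 schedules an assessment of co-interventions at 8 weeks, 12 weeks and 12 weeks after treatment, without saying what it asks.

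**The concern.** The protocol regards organized yoga as a problem at entry, but once women are randomized it neither asks controls to avoid it nor specifies asking them about it. Uptake is plausible. Every participant has incontinence and has been told that the study compares yoga with physical conditioning for managing it (Section 5.2, Overview). Control classes end at week 12, with outcomes still to be collected at week 24. The control program was built to leave out pelvic floor engagement and mindful relaxation, so outside yoga would work against the intended contrast.

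At stake is the interpretation of the pilot's main quantitative product. Section 9.8 compares the between-group differences across weeks to judge trend and persistence, and Sections 1 and 9.2 pass the difference on to the planning of a full-scale trial. If the week-24 difference is smaller than the week-12 difference, two explanations compete: the benefit of yoga has faded, or some controls have started yoga. Without a record the team cannot choose between them.

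**Working it through.** **1. Where outside yoga is addressed**

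| Place | Yoga arm | Control arm |
|---|---|---|
| Entry (4.2) | excluded if organized and within 3 months | same |
| Inclusion commitment (4.1) | medical treatments only | same |
| Home practice (5.1, 5.2) | discouraged | not mentioned |
| Prohibited list and query (5.3.2) | not named | not named |
| Self-management query (5.3.1) | pamphlet techniques only | same |
| Prior yoga experience (6.1.5, item D) | screening/baseline only | same |
| Co-intervention row (6.2.7) | content undefined | content undefined |

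The home practice logs in Section 5.4 track assigned practice for adherence. They could pick up outside yoga by chance, but they are not designed to.

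**2. Size of the possible dilution**

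The documents give no crossover rate, so both inputs are assumptions: c, the fraction of controls who take up yoga, from 5% to 20%; and f, the share of the study program's effect that they gain, 0.5 or 1. If these women would otherwise respond like other controls, and the yoga arm is unaffected, the control mean moves toward the yoga mean by c × f of the true difference:

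observed difference = (1 − c × f) × true difference

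| c | f = 1 | f = 0.5 |
|---|---|---|
| 5% | 95% | 97.5% |
| 10% | 90% | 95% |
| 20% | 80% | 90% |

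**3. What this does to the reading of persistence**

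Suppose that the true difference is the same at weeks 12 and 24, that no control woman does yoga by week 12, and that 20% do by week 24. The observed difference then falls by 0.20 × 0.5 = 10% (f = 0.5) to 0.20 × 1 = 20% (f = 1). A true loss of 10% to 20% of the effect with no crossover would give the same estimates. Only a record of outside yoga by arm separates the two.

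**4. Set against the pilot's precision**

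With about 45 women per arm (Section 9.2), an unadjusted 95% interval for a difference in means has a half-width of 1.96 × √(2/45) = 0.41 SD. If the true effect were 0.5 SD (an assumption), a 10% dilution is 0.05 SD and a 20% dilution is 0.10 SD, both well inside sampling error.

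The plan states no power or sample size derivation, so there is no figure of its own to reproduce.

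**The case against.** Several stronger readings are tempting, and the documents do not support them.

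- *Controls could take up the experimental treatment itself.* The treatment is a specific package: selected Iyengar postures with attention to the pelvic floor, instructors trained by the study's consultants, two 90-minute classes a week and a study manual. Community yoga is not that, so f is probably below 1. A practitioner-led yoga program aimed at incontinence might even fall under Section 5.3.2, since its list is introduced as examples.
- *Such uptake would go unrecorded.* This is unproven. The content of the co-intervention form is not defined and the forms are not in the documents. What can be said is that no specified item asks.
- *Section 5.1 contains a contamination rule that was left out of one arm.* Its stated reason is fidelity to the study technique, which concerns women learning that technique.
- *The future trial would be inflated by a known amount.* Sizing a trial on the diluted difference would multiply the sample size by 1/(1 − c × f)², that is 1.11 to 1.56 for c = 5% to 20% at f = 1. But c and f are assumed, f = 1 is the worst case, and Section 9.2 fixes the target at a 25% greater reduction, with the pilot data as a guide.

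It is also fair to say that uptake may be low during weeks 1 to 12. Controls already commit to two classes and an hour of home practice a week, are confirmed as available and willing before randomization, and have had no recent organized yoga. The pilot is expressly not powered for efficacy.

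All of this limits the size of the problem. It does not close the gap: followed as written, the plan neither asks controls to avoid outside yoga nor specifies asking whether they did it, through week 24.

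**Conclusion.** The point holds in a limited form. The asymmetry after randomization and the lack of a specified follow-up item are plain in the text. The consequence is a possible narrowing of the between-group difference, most likely after week 12, that the planned data could not distinguish from loss of effect. How much narrowing is unknown. The illustrative range is 2.5% to 20% of the true difference, which rests on assumed uptake of 5% to 20% and an assumed gain of half to all of the effect. Within this pilot such a shift would be small beside sampling error, so it is a cheap improvement and not a threat to the trial. It is worth making because the pilot is meant to test procedures for a larger trial, and the rate of outside yoga among controls is something that a pilot can learn.

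**What to change.** In Section 5.3.2, extend the request already made in Section 5.1 to both arms: avoid non-study yoga through week 24. As with the other items there, a woman who does otherwise stays in the study. Define the co-intervention assessment in Section 6.2.7 so that it asks every participant about non-study yoga at 8, 12 and 24 weeks, and add to Section 9.8 that the proportions will be reported by arm beside the between-group differences.

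The cost is a few lines of protocol text, one form item and a non-binding request to control women. A request to avoid new conditioning classes is not supported by anything shown here and would restrict ordinary exercise; at most, such classes could be recorded on the same form.
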